Following consent and prior to completing community/home-based Intervention/Experimental EMAs, participants will undergo standardized testing and smart device training. PWA will be pseudorandomly assigned to either the 1-item or 9-item EMA condition, counterbalanced for aphasia severity. Next, PWA will complete the three-week community/home-based EMA protocol. Each day, PWA will be scheduled to attempt naming aloud 36 pictures that appear on the smartwatch, either delivered either as a single trial 36 times per day (1-item EMA condition) or in four sets of nine trials/set per day (9-item EMA condition). During the EMA period, participants will complete a brief survey about their EMA experiences at the end of each week. Following completion of the EMA protocol, participants will complete one final assessment and exit interview session.

Study Duration*: 1 year **Participant Duration:** 5-6 weeks

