5 STUDY POPULATION

5.1 INCLUSION CRITERIA

Inclusion criteria include: (1) current/pre-stroke English proficiency, (2) normal/corrected-to-normal vision and hearing, (3) medical stability, (4) history of left hemisphere stroke at least six months prior to enrollment, and (5) presence of aphasia as determined by consideration of scores on language assessments (e.g., Quick Aphasia Battery, discourse tasks) and the study team's clinical judgment.

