Retention Team, we will also develop and implement strategies to ensure recruitment of participants of color. One strategy will be to maximize engagement with Hispanic/Latinx and Asian PWA involved in an active clinical trial conducted by the BU Aphasia Research Lab on bilingual aphasia recovery. Given our multipronged approach, the large pool of potential participants, and expected high interest in the study, we anticipate having a waitlist of potential participants. Thus, a second approach will be to prioritize participation of PWA of color on the waitlist to ensure their necessary inclusion in this study. All efforts will be made to maximize retention of enrolled participants. We will do so by: (1) careful screening of potential participants in which we explain in detail the procedures (e.g., protocols, time commitment) and provide time and opportunity for addressing the questions/concerns of participants and/or care providers, (2) providing flexible scheduling options and assistance with arranging transportation as needed, and (3) weekly contacts in weeks 2-4 during the EMA/μEMA protocols with PWA and/or their care providers.

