6 STUDY INTERVENTION(S) OR EXPERIMENTAL MANIPULATION(S)

6.1 STUDY INTERVENTION(S) OR EXPERIMENTAL MANIPULATION(S) ADMINISTRATION

6.1.1 STUDY INTERVENTION OR EXPERIMENTAL MANIPULATION DESCRIPTION

Participants will be pseudo-randomly assigned to either the 1-item EMA condition (n = 10) or 9-item EMA condition (n = 10). For every prompt, the smartwatch will vibrate to alert the participant to a prompt to complete either a single picture naming trial (in the 1-item condition) or a set of picture naming trials (in the 9-item EMA condition). Participants in both conditions will be scheduled to complete 36 overt picture naming trials per day for three weeks. The only difference between conditions will be the trial delivery schedule: PWA in the 1-item condition will complete a single naming trial at a time, 36 times per day whereas PWA in the 9-item EMA condition will receive four prompts per day to complete a set of nine picture naming trials per prompt. The twofold rationale for comparing 1-item and 9-item EMA conditions is that we will be able to ensure the results reflect the viability of either delivery schedule specifically and not just the novelty of smartwatch use, and this approach will provide preliminary data regarding which method works best for which PWA.

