6.3 MEASURES TO MINIMIZE BIAS: RANDOMIZATION AND BLINDING

PWA will be pseudo-randomly assigned to either the 1-item or 9-item EMA condition. This quasi-randomization will be done to ensure the conditions are balanced for overall aphasia severity. No blinding will be performed.

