8.1 ENDPOINT AND OTHER NON-SAFETY ASSESSMENTS

Endpoint Assessments: Feasibility will be classified in three ways: (1) PWAs' adherence to the smartwatch μΕΜΑ or EMA protocol via compliance and completion, (2) PWAs' perceived burden of completing the EMA protocol, and (3) speech intelligibility of recorded naming attempts. Currently, PWAs' capacity for adhering to a smartwatch EMA protocol via button press responses or verbal responses is unknown. As such, compliance will be based on the number of YES button responses to the "Ready?" screen whereas completion will be based on naming attempts. Specifically, similar to [name] et al. (2016), compliance will be determined by the number of YES responses over scheduled trials, including trials missed due to the watch being off/uncharged. Completion will be calculated as trials with captured audio (reflecting attempted naming) over delivered trials, excluding trials missed to the watch being off/uncharged. Perceived burden will be measured via responses to the weekly surveys during weeks 2-4. Finally, speech intelligibility will be measured by a categorical rating of responses captured in each audio clip (i.e., completely intelligible, partially intelligible, or completely unintelligible).

Other Non-Safety Assessments: Before the EMA period, PWA will be administered the following testing battery. The Quick Aphasia Battery (QAB) will be used as our eligibility assessment and to measure overall aphasia severity. The Pattern Comparison Processing Speed Test and Flanker Inhibitory Control and Attention Test from the NIH Cognition Toolbox will be used to measure non-linguistic visual attention and executive functions, respectively. We will use brief, standardized picture description and story elicitation tasks from the AphasiaBank protocol to index anomia in discourse. Participants will complete an overt object naming test twice before EMA and once after EMA so that the research team can evaluate word retrieval via the standard SLP assessment format (i.e., single administration in a quiet 1:1 interaction). This picture naming probe will include normed real photos of the 260 items from the Snodgrass and Vanderwart stimuli set. Before EMA, PWA will also participate in an intake interview and complete a questionnaire about their comfort with technology, adapted for aphasia (simple language, short phrases).

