9 STATISTICAL CONSIDERATIONS

9.1 STATISTICAL HYPOTHESES

- Primary Efficacy Endpoint(s): Compliance and completion will be significantly higher for participants who complete the 1-item EMA condition versus participants who complete the 9-item EMA condition.
- Secondary Efficacy Endpoint(s): Speech intelligibility will be over 80% across trials. Perceived burden will not significantly differ between participants who complete the 1-item versus 9-item EMA conditions.

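### Section 6.3 assigns condition by quasi-randomization with no stated random element, concealment or eligibility lock, so selection bias in the primary 1-item versus 9-item contrast cannot be excluded

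*Combined protocol and SAP*

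**What the plan says.** - **Allocation.** Section 6.3, the protocol's section on minimizing bias, calls the assignment pseudo-random and adds: "This quasi-randomization will be done to ensure the conditions are balanced for overall aphasia severity. No blinding will be performed". The synopsis (1.1) says: "PWA will be pseudorandomly assigned to either the 1-item or 9-item EMA condition, counterbalanced for aphasia severity". Section 6.1.1 sets the groups at 10 and 10. No section gives a sequence method, block size, severity cut-offs, a concealment step, or the person who holds or applies the assignment.
- **Eligibility.** Section 5.1 determines the presence of aphasia from language scores, without a cut-off, "and the study team's clinical judgment". Section 8.1 states: "The Quick Aphasia Battery (QAB) will be used as our eligibility assessment and to measure overall aphasia severity". One score therefore serves both the entry decision and the balancing.
- **Timing.** The synopsis lists assignment after testing and smart device training. In the Schedule of Activities (1.3), the last part of that training, the simulation in a distracting environment, already differs by condition. Nothing says that eligibility is closed before the condition is known.
- **Primary hypothesis.** Section 9.1: "Compliance and completion will be significantly higher for participants who complete the 1-item EMA condition versus participants who complete the 9-item EMA condition". The primary model (9.4.2) contains condition and random effects of participant and trial, with no baseline covariate.

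**The concern.** Concealment matters most where entry involves judgment. If whoever accepts a candidate can work out which condition comes next, acceptance or deferral can come to depend on it, even without intent. The groups may then differ in how likely their members are to answer prompts, whatever the delivery schedule does.

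Here one score informs both entry and balancing, earlier assignments are open, and the group sizes are fixed. Each gives some information about the next condition unless the procedure withholds it, and no such procedure is described. The stated hypothesis also favours one condition.

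Balancing on severity does not cover everything that may affect response. Section 5.3 names severe hemiparesis and, in severe aphasia, lack of a care partner as possible difficulties. Section 9.4.9 treats age, cognition and comfort with technology as possible correlates of feasibility. The primary test compares conditions, and 6.1.1 wants preliminary data on which schedule suits whom; both need comparable groups.

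**Working it through.** **1. Benchmark: the plan's own figure (9.2).** Inputs: 10 per group, 756 trials each, AR(1) correlation 0.6, alpha 0.05, reference proportion 0.500, odds ratio 1.20.
- Second proportion: 1.20/(1 + 1.20) = 0.545, a difference of 0.045.
- AR(1) design effect: 1 + 2 × Σ(1 − k/756) × 0.6^k, for k = 1 to 755, = 3.990.
- Effective trials per group: 10 × 756/3.990 = 7560/3.990 = 1894.7.
- Two-sided power for 0.500 versus 0.545: 80.0%. The stated 80% reproduces. The present point does not alter it; 0.045 serves only as a yardstick.

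**2. How predictable could assignment be?** The documents specify no algorithm, so the schemes below are assumptions. Each was simulated for 20 sequential entrants (3000 runs), with a guesser who knows the scheme and all earlier assignments. Ranges cover one to three equally likely severity strata, except in the forced 10:10 row, which has none.

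| Scheme | Average chance of a correct guess | Assignments known for certain |
|---|---|---|
| Simple randomization | 50% | 0% |
| Only a forced 10:10 total | 61.5% | 8.9% (about 1.8 of 20) |
| Stratified blocks of 10 | 59–65% | 4–17% |
| 80% biased coin on severity | 67–68% | 0% |
| Stratified blocks of 4 | 68–71% | 27–33% |
| Blocks of 2, or deterministic severity balancing | 73–75% | 46–50% |
| Strict alternation | 97.5% | 95% |

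Two entries can be checked by hand. Under deterministic balancing in one stratum, every second assignment is forced and the others are a coin toss: (0.5 + 1)/2 = 0.75. Under alternation only the first is unknown: (0.5 + 19)/20 = 0.975.

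**3. What could that do to the contrast?** Suppose acceptance decisions shift an entrant's expected compliance by +d when the 1-item condition is guessed and −d when the 9-item condition is guessed. With a correct-guess probability g, the 1-item mean moves by d(2g − 1) and the 9-item mean by −d(2g − 1). The spurious difference is 2d(2g − 1). With d = 0.05 (assumed):
- g = 0.50: 0
- g = 0.615: 2 × 0.05 × 0.23 = 0.023
- g = 0.75: 2 × 0.05 × 0.50 = 0.05
- g = 0.975: 2 × 0.05 × 0.95 = 0.095

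The result is proportional to d, for which the documents give no value.

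**The case against.** **The judgment is narrow.** In 5.1 clinical judgment bears on whether aphasia is present. A borderline candidate is therefore mildly affected, and severity is the factor being balanced. Section 5.3 says that people with severe aphasia and no care partner are not shut out and that hemiparesis is accommodated; comfort with technology is not an entry criterion. This limits the room for selection. It does not close it, because people of equal severity still differ in other ways that affect response.

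**This is a 20-person feasibility pilot with automatic capture (6.2.1).** Automatic recording protects the measurement of compliance and completion, and open delivery is unavoidable with these schedules. Neither bears on who enters which arm. The defect is missing concealment, not missing blinding.

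**Stronger readings that a reader might draw, and that the documents do not support:**
- *The people who judge eligibility also allocate, and can foresee the condition.* One lab and no named independent party make this plausible, but the allocator is never identified and predictability depends on the unstated algorithm.
- *The waitlist lets the team pick entrants to suit the next slot.* Section 5.5 says only "we anticipate having a waitlist of potential participants", and its one stated rule is demographic: "a second approach will be to prioritize participation of PWA of color on the waitlist". Study testing follows consent, so nothing gives the team a study QAB score for people still waiting.
- *One misplaced pair shows the size of the bias.* Exchanging a 0.90 and a 0.50 complier between arms of 10 moves the difference by 2 × 0.40/10 = 0.08. Both values are assumed, and accepting or deferring someone is not an exchange. If participants were half at each value, the SD would be 0.20 and the chance standard error 0.20 × √(2/10) = 0.089, so properly concealed randomization would often produce as much.
- *No analysis could repair it.* Severity, age, cognition and comfort with technology are collected (9.4.5, 9.4.9) and could enter the model. With 20 people adjustment would be limited, and it would not reach unmeasured factors.

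**Conclusion.** The point holds as a design weakness that should be changed. The plan names a weaker form of allocation than it needs and provides no concealment or eligibility lock, while its primary hypothesis is a between-condition test. Selection bias is not excluded; it is not demonstrated.

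The size is uncertain. Guessability runs from 50% to 97.5% across plausible schemes. Under the assumed shift of 0.05 either way, the spurious difference is 0 to 0.095. Deterministic severity balancing, one possible reading of the text, gives 0.05. That is about the 0.045 for which the study is powered, but well below the difference of more than 0.20 that 9.2 cites from an earlier study. The upper end needs both strict alternation and entry decisions that act consistently on the guess.

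**What to change.** In 6.3, replace quasi-randomization with concealed random assignment that still balances severity. Examples are minimization on QAB severity with a random element, or randomly permuted blocks of varying size within two QAB strata. Hold it in the REDCap database already planned (10.1.9.1), loaded by an existing team member who does not decide eligibility.

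State the order of events: record final eligibility and the QAB score, then release the condition, and do so before the condition-specific training simulation in 1.3. Align the synopsis with that order.

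The lock and the concealment do most of the work. The table shows that a biased coin or small blocks can still be guessed about two-thirds of the time when earlier assignments are open. Once the entry decision is recorded first, a guess has much less to act on, but decisions made before that record, such as whom to assess and when, can still respond to it; the random element limits this.

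The cost is a one-time REDCap set-up and a few sentences of text, with no extra staff. Severity balance may be slightly less exact than with hand balancing, and the final split may depart a little from 10:10.

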6.2.1 INTERVENTIONIST TRAINING AND TRACKING

N/A - There is no intervention as part of this trial. Data used to calculate compliance, completion, and perceived burden will be automatically digitally recorded. Speech intelligibility ratings will be completed for all samples by one rater, and 20% of samples will be assessed by a second rater.

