9.4.3 ANALYSIS OF THE SECONDARY ENDPOINT(S)

Every audio clip (n trials will vary by person, depending on the number of naming attempts) will be coded as 0 for completely or partially unintelligible and 1 for completely intelligible, reflecting speech intelligibility. We will run a logistic mixed effects model with intelligibility as the dependent variable, condition (1-item vs. 9-item) as the independent variable, and random effects of participant and trial. For perceived burden, we will collect responses on three questions/survey for three weeks. Given the small amount of data, survey responses will be plotted to visualize trends in increasing/decreasing burden rather than compared statistically. We will statistically compared averaged burden ratings between participants in the 1-item vs. 9-item condition using t-tests or Wilcoxon rank sum tests (depending on the distribution of the data).

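### Intelligibility is compared between conditions on human ratings, but the no-blinding statement makes no exception for the raters; masked, shuffled clips would protect that comparison at little cost

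*Combined protocol and SAP*

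**What the plan says.** Four parts of the combined protocol and SAP bear on this.

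- **Blinding.** Section 6.3, on measures to minimise bias, describes the pseudo-random assignment and then says "No blinding will be performed". It does not separate participants and coordinators from those who score outcomes.
- **Who scores what.** Section 6.2.1 says "Data used to calculate compliance, completion, and perceived burden will be automatically digitally recorded". For intelligibility it says "Speech intelligibility ratings will be completed for all samples by one rater, and 20% of samples will be assessed by a second rater". Neither rater is said to be masked, and the raters are not identified.
- **What the rating is.** Under 8.1, "speech intelligibility will be measured by a categorical rating of responses captured in each audio clip", with three levels. Section 9.4.3 collapses these: each clip "will be coded as 0 for completely or partially unintelligible and 1 for completely intelligible, reflecting speech intelligibility".
- **How it is used.** Section 9.4.3 says "We will run a logistic mixed effects model with intelligibility as the dependent variable, condition (1-item vs. 9-item) as the independent variable". The hypothesis in 9.1 is a level: "Speech intelligibility will be over 80% across trials".

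No section describes neutral file names, a shuffled rating order or withholding of the condition from the raters.

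**The concern.** Participants cannot be masked to how often their watch prompts them, so an open design is reasonable for them. That reason does not extend to someone listening to recordings afterwards. The response window is at most five seconds per picture (6.1.2), and a short naming attempt need not disclose the delivery schedule. Labels, dates and playing order can disclose it: nine clips made in close succession point to the 9-item condition.

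The analysed cut lies between fully and partly intelligible, and the documents give no written criteria for it. Borderline clips are where knowledge of condition can act. Any difference in how they are resolved goes directly into the condition effect of the 9.4.3 model, and afterwards it cannot be told apart from a real effect. Double-rating 20% of clips measures agreement between raters. If both know the condition and lean the same way, agreement can be good while the contrast is biased.

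What is at stake is one secondary comparison, in a pilot that aims to learn which delivery schedule suits which participants (6.1.1).

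**Working it through.** **1. Is intelligibility the only rater-scored endpoint?** Section 6.2.1 lists the data for compliance, completion and burden as recorded automatically. Of the feasibility measures in 8.1, that leaves intelligibility. At most 2 x 10 x 756 = 15,120 clips go to the main rater, and 0.20 x 15,120 = 3,024 are rated twice. Actual numbers will be lower, because only captured attempts yield clips.

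**2. The plan's own figure (9.2).** Inputs: 10 per group, 756 repeated measures, AR(1) correlation 0.6, alpha 0.05 (two-sided assumed), reference 0.500, odds ratio 1.20.
- Comparison proportion: 1.2 / 2.2 = 0.5455.
- Design effect: 1 + 2 x sum over k = 1 to 755 of (1 - k/756) x 0.6^k = 3.990.
- Effective observations per group: 10 x 756 / 3.990 = 1,894.7.
- Two-proportion power: 0.800.

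The stated 80% reproduces. Masking alters none of these inputs.

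**3. The same odds ratio at the intelligibility level.** At 80% the odds are 0.80/0.20 = 4.0. Then 4.0 x 1.2 = 4.8, and 4.8/5.8 = 0.828, a difference of about 2.8 points. The 4.5-point difference in 9.2 belongs to a 50% base rate and is not the right yardstick here.

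**4. Size of a rating tilt (assumed values; the documents give none).** Difference between arms = borderline share x gap in the proportion of borderline clips scored intelligible.
- 52.5% v 47.5%: 0.15 x 0.05 = 0.75 points; 0.20 x 0.05 = 1.0 point.
- 55% v 45%: 0.15 x 0.10 = 1.5 points; 0.20 x 0.10 = 2.0 points.
- 60% v 40%: 0.15 x 0.20 = 3.0 points; 0.20 x 0.20 = 4.0 points.

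**5. Effect on the pooled level.** At 55% v 45%, each arm moves from neutral 50:50 scoring by 0.15 x 0.05 = 0.75 to 0.20 x 0.05 = 1.0 point, in opposite directions. With equal clip numbers the shifts cancel. If 60% of clips came from one arm (assumed), the pooled figure would move by at most 1.0 x (0.60 - 0.40) = 0.2 points.

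**6. Effect on the test (assumed values).** Take true intelligibility of 80% in both arms and clips from 70% of trials, so 10 x 756 x 0.7 = 5,292 clips per arm. Divide by 3.990 under AR(1), or by 1 + (529.2 - 1) x ICC for a participant-level intraclass correlation (ICC). A two-sided 5% two-proportion test then gives these chances of a false significant difference:

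| Tilt between arms | AR(1) 0.6, as in 9.2 | ICC 0.05 to 0.20 |
|---|---|---|
| 0 points | 5% | 5% |
| 1 point | 10% | 5-6% |
| 2 points | 26% | 6-8% |
| 3 points | 51% | 7-12% |

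The effect on the p-value depends heavily on the correlation structure. The shift in the estimate does not.

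**The case against.** The case on the other side has real force.

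**Direction.** A reader might infer that raters will favour the 1-item schedule because the team expects it to win. The documents do not support this for intelligibility. Section 9.1 says "Compliance and completion will be significantly higher for participants who complete the 1-item EMA condition", which covers only compliance and completion, and those are recorded automatically. Section 2.2 favours the single-item method for response rate and burden. A tilt is possible in either direction; none is predicted. This stands.

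**The 80% hypothesis.** A reader might also infer that a tilt could carry an arm over the 80% mark. But the hypothesis is set across trials, with no version per arm, and step 5 shows that opposite shifts nearly cancel. General leniency in both arms could inflate the level, and masking condition would not cure that. This stands.

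**Magnitude.** No document gives a borderline share or a tilt, so the figures in steps 4 and 6 only show scale. With participant-level correlation, a 2-point tilt hardly changes the false-positive rate. This stands for the test, but not for the estimate, which is biased regardless.

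**Feasibility of masking.** Research assistants train participants in person (1.3) and the team holds weekly check-ins. A rater drawn from that team might recognise some of 20 voices. This limits the remedy without defeating it, because removing labels, dates and order still closes the most direct route for bias.

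**Weight.** Intelligibility is a secondary endpoint in a small feasibility study, and the second rater would expose scoring peculiar to the main rater. Both are true; a tilt that the raters share would still pass unseen.

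**Conclusion.** The point holds for the between-condition intelligibility contrast. The plan has a subjective outcome, unmasked raters and a planned comparison by condition, and no safeguard links them. Under the assumed 15-20% borderline share and a 55% v 45% split, the bias is 1.5-2 points, against about 2.8 points for an odds ratio of 1.20 at 80%. Smaller tilts give proportionately less. These inputs are assumptions, and the documents show neither that a tilt will occur nor which way it would go.

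The point does not reach compliance, completion or burden, which no rater scores, and it leaves the pooled over-80% hypothesis largely untouched. The plan contains no arithmetic error here. This is a cheap improvement to a secondary endpoint, worth making because biased ratings cannot be corrected later unless the clips are scored again under masking.

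**What to change.** Amend 6.2.1 and 6.3 to state that:

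- participants and coordinators are unblinded;
- both existing intelligibility raters score clips under random file codes, with condition, participant code, date and prompt type removed;
- clip order is mixed across participants and conditions;
- the condition key is withheld until ratings are locked.

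Where the current team allows, use the raters with least participant contact, and report that masking may be incomplete if voices are recognised.

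**Cost.** A renaming and shuffling script and a few sentences. Section 10.1.3 already assigns alphanumeric codes to digital data. That no extra staff are needed is an inference, since the documents do not identify the raters; it holds if the existing raters are kept. Sample size, alpha and visits do not change.

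**Downside.** Raters lose the chance to adapt to one speaker. This should act alike in both conditions, but it may slightly lower the absolute level that is set against 80%, and the report should say so.
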